#### 11.7.2.1. Handling of Missing and Partial Dates

Element	Reporting Detail
General	
 
Partial dates will be displayed as captured in participant listing displays.
 
Dates which are completely missing will not be imputed, with the exception of the treatment stop date. Details for imputation of the treatment stop date are provided below.
 

Study treatment start and stop date	
 
If the study treatment start date is missing, the Visit 3 (Day 1) date will be used.
 
If overall treatment stop date is missing or partial, it will be imputed as follows: 
 
For participants who attended an Early Withdrawal visit, use the date of the Early Withdrawal visit
 
For participants who attended the last on-treatment visit, use the End of Study Visit date
 
For participants who died and did not attend the last on-treatment visit, use the date of death
 
For all other participants, use the last recorded exposure stop date
 
 
 

Adverse Events	
 
Partial dates were not permitted to be entered in the eCRF for AEs, therefore no imputation of AE dates will be performed.
 

 

Concomitant Medications	
 
Partial dates for any concomitant medications will be imputed using the following convention: 
 
If the partial date is a start date, a '01' will be used for the day and 'Jan' will be used for the month
 
If the partial date is a stop date, a '28/29/30/31' will be used for the day (dependent on the month and year) and 'Dec' will be used for the month.
 
 
 
The recorded partial date will be displayed in listings.
 

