4. STUDY DESIGN

4.1. Overall Design

This study employs a multi-centre, active-controlled, double-blind, parallel-group design. At the conclusion of the 3-week run-in period (Visit 2), all subjects who meet the pre-defined criteria will be enrolled to receive FF/VI (100/25 mcg via the ELLIPTA dry powder inhaler [DPI]) once a day, in the morning, during the 2-week stabilization period. At the conclusion of the stabilization period (Visit 3), all subjects who meet the pre-defined criteria will be randomised 1:1:1:1:1 to receive either FF/UMEC/VI (100/31.25/25; 100/62.5/25; 200/31.25/25; 200/62.5/25 mcg) or FF/VI (100/25; 200/25 mcg) via the ELLIPTA DPI once daily in the morning for the duration of the treatment period (see Section 4.2 for further details on study treatment assignment and duration).

Subjects who permanently discontinue study treatment are not required to withdraw from the study. Subjects who have permanently discontinued study treatment and have not withdrawn consent are encouraged to continue in the study and complete all remaining protocol specified clinic visits (see Section 5.6).

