5.6. Withdrawal/Stopping Criteria

5.6.1. Withdrawal from Study Treatment

Subjects who withdraw from double-blind study treatment prematurely (for any reason) should, where possible, continue to be followed-up as per protocol until the completion of the Safety Follow-up assessments (Section 7.1; refer to the SRM for further details). If this is not possible, the Investigator must encourage the subject to participate in as much of the study as they are willing (or able) to.

A subject may be withdrawn from study treatment at any time. A reason for premature discontinuation of study treatment (e.g., AE, lack of efficacy [including acute moderate or severe asthma exacerbation], protocol deviation, Investigator discretion, consent withdrawn etc.) must be captured in the eCRF.

A subject must be withdrawn from study treatment if any of the following stopping criteria are met:

- Liver Chemistry: Meets any of the protocol-defined liver chemistry stopping criteria (see Section 5.6.3 and Appendix 2)
- QTc: Meets any of the protocol-defined stopping criteria (see Section 5.6.4)
- Pregnancy: Positive pregnancy test (see Section 7.5.3 and Appendix 5)

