				Fixed Treatment Period			Variable Treatment Period			Early Withdrawal (EW) ⁴	Safety Follow-up Contact
Visit	0	1 ¹	2 ²	3 ³ Randomization	4	5	6	7	8 End of Study (EOS)		
Study Day	-49 to -36	-35	-14	1	29	85	169	253	365		
Week	-6 to -7	-5	-2	0	4	12	24	36	52		1 week after Visit 8/EOS or EW Visit
Window					-5/+2d	-5/+2d	-5/+2d	-5/+2d	-5/+2d		-1/+4d
Collect double-blind study treatment (Scheduled)					x	x	x	x	x	x	
Collect double-blind study treatment (Unscheduled)				x ²⁹							
Dispense albuterol/salbutamol, as required		x	x	x	x	x	x	x			
Collect albuterol/salbutamol, as required			x	x	x	x	x	x	x	x	
Dispense FP, as required ³⁰		x	x	x	x	x	x	x			
Collect FP, as required			x	x	x	x	x	x	x	x	

Notes:

1. Visit 1 should be completed ≥ 1 day but ≤ 14 days after Visit 0; however, if it is local and routine medical practice to request that a subject withhold their ICS/LABA medication for at least 24 hours prior to a clinic visit then, provided that the subject has complied with the request, Visit 0 and Visit 1 can occur on the same day.
2. Visit 2 may be conducted up to 3 days before the scheduled date of Visit 2. The duration of the run-in period (i.e. the time period between Visits 1 and 2) must be ≥ 18 days but ≤ 26 days.
3. Visit 3 must always be conducted ≥ 14 days but ≤ 17 days after Visit 2.
4. EW Visit should be conducted if double-blind study treatment is discontinued AND the subject discontinues from participating in the study.
5. The ICF must be signed before any study procedures, including protocol-specified medication cessation.
6. Genetics research consent may be obtained at the same time as the study IC and must be obtained prior to obtaining a genetic blood sample.

7. The assessment of asthma history will include: the age of the subject when they were first provided with an inhaler for asthma; completion of an asthma medical history questionnaire (a copy of this questionnaire and instructions for its use can be found in the SRM).
8. Subjects must not be randomised prior to confirming their eligibility to participate in the study.
9. The IRT will be used for randomization, emergency unblinding and study treatment supply management (Please refer to the RAMOS NG IRT manual and SRM for more information).
10. Assessment(s) to be completed prior to the administration of study treatment.

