7.3.5. Daily Diaries

Subjects will be issued with a combination spirometer and eDiary device at Visit 1 for twice daily use (in the morning upon waking and in the evening just before going to bed) throughout the study. The eDiary device will be provided by a third-party vendor. Information on the device and its use are documented in the SRM and the third-party vendor manual. Subjects will be instructed on how to use the device in order to record results for the following in the eDiary each day from Visit 1 onwards:

- Daily symptom assessment (E-RS and supplemental asthma items; night-time awakening, asthma symptom and physical activity questions)
- The number of inhalations of rescue albuterol/salbutamol used during the day and night.
- Morning and evening FEV₁
- Morning and Evening Peak Expiratory Flow (PEF)

- Morning and evening FSC medication use (during the run-in period only)
- Morning FF/VI medication use (during the stabilization period only)
- Morning double-blind study medication use (during the treatment period only)

Section 7.3.5.1 describes the assessments and questionnaires recorded on the eDiary device, as well as the alerts that can be triggered based on recorded results. The data from the eDiary device will be automatically transmitted to a centralised server on a daily basis. The Investigator and designee(s) will be provided with access to the transmitted eDiary data via a vendor-provided portal and should review the data on an ongoing basis to check for the incidence of alerts (see Section 7.3.5.1.6) as well as subject compliance with eDiary use and study treatment administration.

Subjects will also be issued with a paper Medical Problems/Medications Taken worksheet to record medical problems experienced and medications used during the study (please refer to the SRM for further details). Subjects must also use this paper worksheet to record all healthcare contacts that occur during their participation in the study. This paper worksheet will be used to assist subject recall in discussions with the Investigator, for site staff to then enter as appropriate in the eCRF.

7.3.5.1. eDiary Questionnaires, Assessments and Alerts

For information on the eDiary questions, please refer to [Appendix 6](#).

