
 
• Treatment Exposure will be summarized as continuous, and using the following categories:             
 
○ <math>\geq 1</math> day, <math>\geq 4</math> weeks, <math>\geq 8</math> weeks, <math>\geq 12</math> weeks, <math>\geq 16</math> weeks, <math>\geq 20</math> weeks, <math>\geq 24</math> weeks, <math>\geq 28</math> weeks, <math>\geq 32</math> weeks, <math>\geq 36</math> weeks, <math>\geq 40</math> weeks, <math>\geq 44</math> weeks, <math>\geq 48</math> weeks and <math>\geq 52</math> week, 24 weeks (-5/+2 days), 36 weeks (-5/+2 days), 52 weeks (-5/+2 days)
 
○ 24 weeks (-5/+2 days) will be based on Day 169. 36 weeks (-5/+2 days) will be based on Day 253. 52 weeks (-5/+2 days) will be based on Day 365.                 
 
○ Subjects whose planned End of Study visit is Week 36 or 52, are included if their Week 24 visit falls within the protocol permitted visit window and they are still on study treatment at this visit.
 
○ Subjects whose planned End of Study visit is Week 52, are included if their Week 36 visit falls within the protocol permitted visit window and they are still on study treatment at this visit.
 
 
 
 
 

Post-treatment On-Study Duration

 
• Post-treatment On-Study duration will be summarized as continuous and using the following categories:             
 
○ Duration (Week): (0, 4], (4, 12], (12, 24], (24, 36], > 36
 
 
 

Adverse Events	
Adverse Event Rate	

 
Event rate per thousand person-years will be displayed on most On-Treatment AE data displays listed in Section 11.10.8. Event rate per thousand person-years will be calculated as the number of events x 1000 divided by the total participant exposure during the time-period of interest.
 
	
On-treatment adverse events by time in study	

The following data/participants with data will be included in the AE summaries for specific time periods. Exposure for the time periods will also be calculated as defined below to allow the presentation of rates.
	
Time point	Data to be included

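### A missing or partial treatment stop date is set to the Early Withdrawal visit date even for participants who stopped drug earlier and stayed in follow-up

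*SAP*

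**What the plan says.** SAP 11.7.2.1 introduces the rule with "If overall treatment stop date is missing or partial, it will be imputed as follows". Participants with an EW visit come first: "For participants who attended an Early Withdrawal visit, use the date of the Early Withdrawal visit". Two further rules use the End of Study (EOS) visit date and the date of death. The last is residual: "For all other participants, use the last recorded exposure stop date". Nothing in the EW rule asks whether drug had been stopped earlier or whether part of the date is known.

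The Protocol (7.1, note 4) defines the EW visit by study exit: "EW Visit should be conducted if double-blind study treatment is discontinued AND the subject discontinues from participating in the study". Protocol 4.1 says that participants who permanently stop drug are "encouraged to continue in the study and complete all remaining protocol specified clinic visits".

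SAP 11.6.1 sorts premature discontinuers into three groups: those who stop drug and study together; those who have only an EW visit and a safety follow-up visit on or after stopping; and those who attend a scheduled visit on or after stopping. Only the third group is treated as continuing in the study. SAP 11.6.4 summarises post-treatment time on study in categories that run past 36 weeks.

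**The concern.** The EW rule assumes that drug stop and study exit coincide. The design separates them on purpose. A participant in the third group who later leaves through an EW visit, and whose stop date is missing or partial, is treated as dosed up to the day of exit.

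The stop date then feeds several results:

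- exposure duration and the person-year denominators (SAP 11.6.4);
- the on-treatment window, which decides which events and assessments enter the on-treatment safety tables (SAP 8, 11.4);
- compliance (SAP 11.6.2) and the curve for time to treatment discontinuation (SAP 6.1);
- the on-treatment (de jure) FEV1 and exacerbation analyses (SAP 7.1.6, 7.2.6, 11.6.3).

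The treatment of partial dates is also uneven. In the same section, a partial concomitant-medication date keeps its recorded part and only the gaps are filled. A partial study-drug stop date is overwritten.

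**Working it through.** The plan states no figure that depends on this rule, so there is nothing to reproduce. I applied the SAP's own formulas to assumed days, with treatment starting on Day 1.

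**Formulas**

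- Exposure = stop − start + 1 (SAP 11.6.4)
- On-treatment window ends at stop + 1 (SAP 11.4)
- Post-treatment duration = last scheduled clinic visit, EOS or EW − (stop + 1) (SAP 11.6.4)
- Compliance = doses taken ÷ (stop − start + 1) × 100 (SAP 11.6.2)

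**One participant, every daily dose taken up to the real stop**

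| Real stop | EW visit | Real exposure | Imputed exposure | Excess | Compliance, real → imputed |
|---|---|---|---|---|---|
| Day 29 | Day 85 | 29 d | 85 d | 56 d (8 wk) | 100% → 29/85 = 34.1% |
| Day 43 | Day 211 | 43 d | 211 d | 168 d (24 wk) | 100% → 43/211 = 20.4% |
| Day 29 | Day 253 | 29 d | 253 d | 224 d (32 wk) | 100% → 29/253 = 11.5% |
| Day 211 | Day 211 | 211 d | 211 d | 0 | 100% → 100% |

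The last row is the case that the rule handles correctly.

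**Post-treatment duration.** For the second row the real value is 211 − (43 + 1) = 167 days. Under the rule it is 211 − (211 + 1) = −1 day. The last row also gives −1, so an affected participant looks like someone treated to the last visit. SAP 8.1 summarises only participants with at least one post-treatment day, so the off-drug period drops out.

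**On-treatment FEV1.** In the second row the window ends on Day 212 instead of Day 44. The Week 12 and Week 24 visits (Days 85 and 169) fall in between. Two of the three visits in the on-treatment repeated-measures model would hold off-drug values.

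**Partial dates.** If month and year are recorded, any gap above 30 days puts the EW date in a different month, so the imputed date contradicts the record.

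**Arm level.** The number affected is not given, so I show a range. The exposure of 375 participants over 24 weeks is 375 × 24 × 7 ÷ 365.25 = 172.5 person-years.

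- One affected, 4-week gap: 28 ÷ 365.25 = 0.08 person-years, or 0.04%.
- One affected, 36-week gap: 252 ÷ 365.25 = 0.69 person-years, or 0.40%.
- Ten affected: 0.44% to 4.0%.
- Ten affected with 52 weeks of treatment (373.7 person-years): 0.21% to 1.85%.

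Twenty-four weeks is the shortest planned duration, so that base is the unfavourable one. A 36-week gap needs someone followed for more than 36 weeks.

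**Direction.** Off-drug events enter the numerator of an exposure-adjusted rate and off-drug time enters the denominator. The rate rises if events per unit of off-drug time exceed the on-drug rate, and falls if they do not.

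**What does not move.** The primary FEV1 analysis (SAP 7.1.6), the key secondary (7.2.6), and SGRQ, ACQ-7 and E-RS (7.3.5.1) use on- and post-treatment data. Imputation in the missing-data sensitivity analyses starts the day after the EW visit (11.7.2.2).

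**The case against.** The trigger is narrow. The stop date must be missing or partial, drug must have stopped early, the participant must have stayed for scheduled visits, and they must then have left through an EW visit. Protocol 6.6 requires stop dates in the eCRF, and SAP 3.2 puts data cleaning before unblinding. The count could be zero. For the first two groups in SAP 11.6.1 the EW date is exact or a reasonable approximation, and Protocol 6.1 allows a last dose at the EW visit. For simple incidence tables, a longer window can only keep events as on-treatment, which many would call cautious. All of this stands, and it limits the point to a small correction.

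The substitutes also have weaknesses. The SAP shows the discontinuation page only through a yes/no question, so that page may lack the very date that is missing. The last recorded exposure date may belong to an earlier container, and ranking it first could cut off real exposure. eDiary dosing is self-reported. These points count against an automatic replacement.

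None of this rescues the rule for the third group. No other section of either document caps or overrides it, and dosing at the EW visit is optional (Protocol 7.1, note 27), so attendance does not show that drug was still being taken.

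**Conclusion.** The rule as written gives a wrong stop date for participants who stopped drug, attended later scheduled visits and left through an EW visit with a missing or partial stop date. For such a participant the error can be large: 56 to 224 days in the assumed examples with an early stop. At arm level it is small unless several are affected. The days and the number affected are my assumptions.

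A reader might infer more than the documents support:

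- That the main results are at risk. They are not, because every analysis in the testing hierarchy uses data regardless of treatment status.
- That adverse event rates are biased in a known direction. The working shows that they can move either way.
- That the EW date is wrong for EW attendees in general. It suits those who stopped drug and study together.
- That many participants are affected. The documents give no count.

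The 3-hour post-dose FEV1 endpoint is also on-treatment, but it is outside the hierarchy, and SAP 7.3.5.1 reasons that someone off drug cannot provide that measurement. The effect is therefore on exposure, compliance, on-treatment safety and de jure results. This is worth tidying, not a major flaw.

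**What to change.** Amend SAP 11.7.2.1 as follows.

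1. Never impute a stop date outside the recorded month and year of a partial date.
2. Use the EW date, and likewise the EOS or death date, only when there is no record of an earlier permanent stop of study treatment.
3. Where an earlier stop is recorded, impute within the recorded partial date and no later than the first scheduled visit at which the participant is recorded as off treatment. Use the last recorded exposure date, the dated in-clinic doses (Protocol 6.6) and the eDiary dosing record (Protocol 7.3.5) as supporting evidence, not as automatic replacements.

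Reporting how many stop dates were imputed, by arm and by rule, would let a reader judge the effect. The cost is a few SAP lines and minor programming with data that the trial already collects.

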### 11.7.2.2. Handling of Missing Data for Statistical Analysis

The utilization of efficacy data in the statistical analyses are summarized in the table below:

Treatment / Study status	Data status	Data Inclusion for Analysis		
		Primary analysis 'de facto' estimand, without imputation	Supportive analysis 'de Jure' estimand, without imputation	Sensitivity Analysis 'de facto' estimand with imputation
on-treatment	have data	Yes	Yes	Yes: not imputed
post-treatment	have data	Yes	No	Yes: not imputed
post-treatment	missing data	No	No	Yes: imputed

Imputed post-treatment missing data will be imputed from early withdrawal visit date + 1 to planned end of study visit.

See Section [7.1.5](#) and Section [7.2.5](#) on the details for the proposed sensitivity analyses.

**11.8. Appendix 8: Model Checking and Diagnostics for Statistical Analyses**

Endpoints	
 
• Change from baseline in Trough FEV1
 
• Change from baseline in ACQ total score
 
• Change from baseline in SGRQ total score and domain scores
 
• Change from baseline in AQLQ total score
 
• Change from baseline in home daily trough FEV1 over the first 24 weeks of the treatment period
 
• Change from baseline in morning (AM) pre-dose PEF over the first 24 weeks of the treatment period
 
• Change from baseline in evening (PM) PEF over the first 24 weeks of the treatment period
 
• Change from baseline in E-RS Breathlessness scores over Weeks 21-24 (inclusive) of the treatment period
 
• Change from baseline in E-RS Cough & Sputum scores over Weeks 21-24 (inclusive) of the treatment period
 
• Change from baseline in E-RS Chest Symptoms scores over Weeks 21-24 (inclusive) of the treatment period
 
• Change from baseline in the percentage of symptom-free days over the first 24 weeks of the treatment period
 
• Change from baseline in the percentage of rescue medication-free days over the first 24 weeks of the treatment period
 
• Change from baseline in daily rescue medication use over the first 24 weeks of the treatment period.
 
• Change from baseline in Pulse rate
 
• Change from baseline in Systolic BP
 
• Change from baseline in Diastolic BP
 
• Change from baseline in QTcF
 
• Change from baseline in PR Interval
 
• Change from baseline in Heart rate (ECG)
 

Analysis	
 
• MMRM
 


 
• The Kenward and Roger method for approximating the denominator degrees of freedom and correcting for bias in the estimated variance-covariance of the fixed effects will be used. 
 
○ In the event the model fails to run using the KR method, then the residual method will be used instead.
 
 
 
• An unstructured covariance structure for the R matrix will be used by specifying 'type=UN' on the REPEATED line. 
 
○ In the event that this model fails to converge, alternative correlation structures may be considered such as CSH or CS.
 
○ Akaike's Information Criteria (AIC) will be used to assist with the selection of covariance structure.
 
 
 
• Distributional assumptions underlying the model used for analysis will be examined by obtaining a normal probability plot of the residuals and a plot of the residuals versus the fitted values (i.e. checking the normality assumption and constant variance assumption of
 
	

the model respectively) to gain confidence that the model assumptions are reasonable].

Endpoints	
 
• Mean change from baseline in clinic FEV1 at 3 hours post study treatment at Week 24
 
• Mean change from baseline in clinic trough FEV1 over the first 24 weeks of the treatment period
 

Analysis	
 
• ANCOVA
 

 
• Distributional assumptions underlying the model used for analysis will be examined by obtaining a normal probability plot of the residuals and a plot of the residuals versus the fitted values (i.e. checking the normality assumption and constant variance assumption of the model respectively) to gain confidence that the model assumptions are reasonable].
 
	

Endpoints	
 
• Annualized rate of moderate/severe asthma exacerbations
 
• Annualized rate of severe asthma exacerbations
 

Analysis	
 
• Negative binomial regression
 


 
• The fit of the regression models will be examined using “Q-Q” plots of the standardized residuals. Interpretation of these plots will be aided by the addition of simulated envelopes as proposed by Atkinson (Atkinson, 1985).
 
• If the model fails to converge, then the number of severe exacerbations will be fitted as a binary (0, >=1) variable. If the model still fails to converge removal of the covariate for number of severe exacerbations in the previous year will be considered.
 
	

Endpoints	
 
• Time to first moderate/severe asthma exacerbation
 
• Time to first severe asthma exacerbation
 

Analysis	
 
• Cox’s proportional hazard model
 

 
• The proportional hazards assumption will be examined by obtaining the Kaplan-Meier estimates of the survival function S(t) over time separately for each treatment group. Under the assumption of proportional hazards between the treatment groups, ln{-ln[S(t)]} for two groups should be parallel to each other and the distance between them constant. If the curves are approximately parallel, then the proportional hazards assumption is not violated. If these curves cross each other or diverge greatly from the assumption of parallel lines, then the assumption is not met.
 
• The ‘exact’ method for handling ties will be used. If the analysis will not run using the ‘exact’ method, the ‘Efron’ method for handling ties will be used instead.
 
	

Endpoints	
 
• Percent of patients meeting a responder threshold of ≥0.5 points improvement (decrease) from baseline for the ACQ-7 at Week 24
 
• Percent of patients meeting a responder threshold of ≥0.5 points improvement (decrease) from baseline for the ACQ-6 at Week 4
 
• Percent of patients meeting a responder threshold of ≥0.5 points improvement (decrease) from baseline for the ACQ-5 at Week 24
 
• Percentage of patients that have achieved asthma control based on ACQ-7 (i.e. a total score ≤0.75) at both Week 12 and Week 24
 

------------------	---

	
 
• Percentage of patients that have achieved asthma control based on ACQ-6 (i.e. a total score <math>\leq 0.75</math>) at both Week 12 and Week 24
 
• Percentage of patients that have achieved asthma control based on ACQ-5 (i.e. a total score <math>\leq 0.75</math>) at both Week 12 and Week 24
 
• Percent of patients meeting a responder threshold of <math>\geq 4</math> points improvement (decrease) from baseline for the SGRQ total score at Week 24
 
• Percent of patients meeting a responder threshold of <math>\geq 0.5</math> points improvement (increase) from baseline for the AQLQ total score at Week 24
 

Analysis	
 
• Generalized linear model
 

	
 
• The Kenward and Roger method for approximating the denominator degrees of freedom and correcting for bias in the estimated variance-covariance of the fixed effects will be used.             
 
○ In the event the model fails to run using the KR method, then the residual method will be used instead.
 
 
 
• Computation of confidence intervals for the odds ratios is based on the individual Wald tests.
 
• Pearson residuals will be plotted by using PLOTS=PEARSONPANEL option for the model statement in SAS.
 

